4.2.3 Rationale for Dose Selection/Regimen/Modification of Pembrolizumab

An open-label Phase I trial (Protocol 001) is being conducted to evaluate the safety and clinical activity of single agent MK-3475. The dose escalation portion of this trial evaluated three dose levels, 1 mg/kg, 3 mg/kg, and 10 mg/kg, administered every 2 weeks (Q2W) in subjects with advanced solid tumors. All three dose levels were well tolerated and no dose-limiting toxicities were observed. This first in human study of MK-3475 showed evidence of target engagement and objective evidence of tumor size reduction at all dose levels (1 mg/kg, 3 mg/kg and 10 mg/kg Q2W). No MTD has been identified to date. 10.0 mg/kg Q2W, the highest dose tested in PN001, will be the dose and schedule utilized in Cohorts A, B, C and D of this protocol to test for initial tumor activity. Recent data from other clinical studies within the MK-3475 program has shown that a lower dose of MK-3475 and a less frequent schedule may be sufficient for target engagement and clinical activity.

PK data analysis of MK-3475 administered Q2W and Q3W showed slow systemic clearance, limited volume of distribution, and a long half-life (refer to IB). Pharmacodynamic data (IL-2 release assay) suggested that peripheral target engagement is durable (>21 days). This early PK and pharmacodynamic data provides scientific rationale for testing a Q2W and Q3W dosing schedule.

A population pharmacokinetic analysis has been performed using serum concentration time data from 476 patients. Within the resulting population PK model, clearance and volume parameters of MK-3475 were found to be dependent on body weight. The relationship between clearance and body weight, with an allometric exponent of 0.59, is within the range observed for other antibodies and would support both body weight normalized dosing or a fixed dose across all body weights. MK-3475 has been found to have a wide therapeutic range based on the melanoma indication. The differences in exposure for a 200 mg fixed dose regimen relative to a 2 mg/kg Q3W body weight based regimen are anticipated to remain well within the established exposure margins of 0.5 – 5.0 for MK-3475 in the melanoma indication. The exposure margins are based on the notion of similar efficacy and safety in melanoma at 10 mg/kg Q3W vs. the proposed dose regimen of 2 mg/kg Q3W (i.e. 5-fold higher dose and exposure). The population PK evaluation revealed that there was no significant impact of tumor burden on exposure. In addition, exposure was similar between the NSCLC and melanoma indications. Therefore, there are no anticipated changes in exposure between different indication settings.

The rationale for further exploration of 2 mg/kg and comparable doses of pembrolizumab in solid tumors is based on: 1) similar efficacy and safety of pembrolizumab when dosed at either 2 mg/kg or 10 mg/kg Q3W in melanoma patients, 2) the flat exposure-response relationships of pembrolizumab for both efficacy and safety in the dose ranges of 2 mg/kg Q3W to 10 mg/kg Q3W, 3) the lack of effect of tumor burden or indication on distribution behavior of pembrolizumab (as assessed by the population PK model) and 4) the assumption that the dynamics of pembrolizumab target engagement will not vary meaningfully with tumor type.

The choice of the 200 mg Q3W as an appropriate dose for the switch to fixed dosing is based on simulations performed using the population PK model of pembrolizumab showing that the fixed dose of 200 mg every 3 weeks will provide exposures that 1) are optimally consistent with those obtained with the 2 mg/kg dose every 3 weeks, 2) will maintain individual patient exposures in the exposure range established in melanoma as associated with maximal efficacy response and 3) will maintain individual patients exposure in the exposure range established in melanoma that are well tolerated and safe.

A fixed dose regimen will simplify the dosing regimen to be more convenient for physicians and to reduce potential for dosing errors. A fixed dosing scheme will also reduce complexity in the logistical chain at treatment facilities and reduce wastage.

4.2.4 Rationale for Endpoints

4.2.4.1 Efficacy Endpoints

1. The primary endpoint is the 1-year RFS rate.
2. The secondary endpoints include median RFS, 3-year OS rate, median OS time, 3-year RFS rate, safety and toxicity.

4.2.4.2 Biomarker Research

1. Tumor tissue part:
 - a. Pre-treatment tumor tissue (i.e., esophagectomy tissue following preoperative cisplatin-based CRT) is mandatory for biomarker study accompanying with the clinical trial. The biomarker study will evaluate the following immune biomarkers in tumor microenvironment:
 - IHC of PD-L1 expression in tumor cells and in tumor-infiltrating immune cells. IHC for different lineages of tumor-infiltrating immune cells (phenotype), including activated CD8+ T cells, regulatory T cells, natural killer cells, suppressor CD4+ T cells, tumor-associated macrophages and myeloid derived suppressor cells.
 - Immune related GEP by NanoString technology
 - Immune repertoire of tumor (deep sequencing for CDR3 region of TCR)
 - Mutation analysis of tumor (targeted genes sequencing or WES)
 - b. The potential biomarkers will be correlated with patients' RFS and OS.
 - c. If recurrent disease is noted, the recurrent tumor tissues will be procured for biomarker study in comparison with the corresponding pre-treatment tumor tissues (optional).
2. Peripheral blood part:
 - a. Blood sample collection is optional for biomarker study accompanying with the clinical trial. The biomarker study will evaluate the following immune biomarkers in peripheral blood:
 - Critical cytokines (such as IL-2, IL-6, IL-8, IL-9, IL-10, IL-17, IL-21, interferon-gamma, transforming growth factor-beta, et al).
 - PD-L1 (enzyme-linked immunoassay for PD-L1 in serum).
 - Immune repertoire of peripheral blood (deep sequencing for CDR3 region of TCR) for correlation with tumor part.
 - Circulating cell-free DNA (targeted sequencing of genomic alterations of interest) for correlation with the mutation analysis of tumor.
 - b. The potential biomarkers in peripheral blood will be correlated with patients' RFS and OS.

5.0 METHODOLOGY

5.1 Entry Criteria

5.1.1 Diagnosis/Condition for Entry into the Trial

1. Histologically proven squamous cell carcinoma of esophagus.

5.1.2 Subject Inclusion Criteria

In order to be eligible for participation in this trial, the subject must:

1. Be willing and able to provide written informed consent/assent for the trial.
2. Be ≥ 20 years of age on day of signing informed consent.
3. Be diagnosed by pathology or cytology with a locally advanced ESCC, which is clinically stage according to the TNM system of the American Joint Committee on Cancer (AJCC) Cancer Staging System (8th edition), fulfilling one of the following criteria as determined by endoscopic ultrasound, computed tomography, bronchoscopy and positron emission tomography:
 - a. T3, N0, M0;
 - b. T4a, N0, M0;
 - c. T1–4a, N1-3, M0.
4. Have been treated with preoperative cisplatin-based CRT followed by esophagectomy with lymph node dissection for the locally advanced ESCC (defined by above criteria).
5. Have a performance status of 0 or 1 on the ECOG Performance Scale.
6. Exhibit at least one risk factor of tumor recurrence in the post-CRT surgical tissues:
 - a. Close (≤ 1 mm) or involved margin;
 - b. Residual tumor cells in lymph nodes with ENI.
 - c. ypN2-3
7. Demonstrate adequate organ function as defined in
8. Table 1, all screening labs should be performed within 10 days of treatment initiation.

Table 1 Adequate Organ Function Laboratory Values

System	Laboratory Value
Hematological	

Absolute neutrophil count (ANC)	≥1,500 /mcL
Platelets	≥100,000 / mcL
Hemoglobin	≥9 g/dL without transfusion or EPO dependency (within 7 days of assessment)
Renal	
Serum creatinine OR Measured or calculated ^a creatinine clearance (GFR can also be used in place of creatinine or CrCl)	≤1.5 X upper limit of normal (ULN) OR ≥60 mL/min for subject with creatinine levels > 1.5 X institutional ULN
Hepatic	
Serum total bilirubin	≤ 1.5 X ULN
AST (SGOT) and ALT (SGPT)	≤ 2.5 X ULN
Albumin	≥2.5 mg/dL
Coagulation	
International Normalized Ratio (INR) or Prothrombin Time (PT)	≤1.5 X ULN unless subject is receiving anticoagulant therapy as long as PT or PTT is within therapeutic range of intended use of anticoagulants
Activated Partial Thromboplastin Time (aPTT)	≤1.5 X ULN unless subject is receiving anticoagulant therapy as long as PT or PTT is within therapeutic range of intended use of anticoagulants

^aCreatinine clearance should be calculated per institutional standard.

9. Female subject of childbearing potential should have a negative urine or serum pregnancy within 72 hours prior to receiving the first dose of study medication. If the urine test is positive or cannot be confirmed as negative, a serum pregnancy[test will be required.
10. Female subjects of childbearing potential (Section 5.7.2) must be willing to use an adequate method of contraception as outlined in Section 5.7.2 – Contraception, for the course of the study through 120 days after the last dose of study medication.

Note: Abstinence is acceptable if this is the usual lifestyle and preferred contraception for the subject.

11. Male subjects of childbearing potential (Section 5.7.1) must agree to use an adequate method of contraception as outlined in Section 5.7.1- Contraception, starting with the first dose of study therapy through 120 days after the last dose of study therapy.

Note: Abstinence is acceptable if this is the usual lifestyle and preferred contraception for the subject.

5.1.3 Subject Exclusion Criteria

The subject must be excluded from participating in the trial if the subject:

1. Is diagnosed with adenocarcinoma of esophagus or gastroesophageal junction.
2. Has synchronously diagnosed with a squamous cell carcinoma of aero-digestive way, other than esophageal cancer.

3. Has prior malignancy, except for: (a) adequately treated basal cell or squamous cell skin cancer; (b) in-situ cervical cancer; (c) previously diagnosed malignancy which have been adequately treated and shown no evidence of recurrence for more than 5 years.
4. Is currently participating and receiving study therapy or has participated in a study of an investigational agent and received study therapy or used an investigational device within 4 weeks of the first dose of treatment.
5. Has a diagnosis of immunodeficiency or is receiving systemic steroid therapy or any other form of immunosuppressive therapy within 7 days prior to the first dose of trial treatment.
6. Has a known history of active TB (Bacillus Tuberculosis)
7. Hypersensitivity to pembrolizumab or any of its excipients.
8. Has not recovered (i.e., \leq Grade 1 or at baseline) from adverse events due to a previously administered agent.
 - Note: Subjects with \leq Grade 2 neuropathy are an exception to this criterion and may qualify for the study.
 - Note: If subject received major surgery, they must have recovered adequately from the toxicity and/or complications from the intervention prior to starting therapy.
9. Has active autoimmune disease that has required systemic treatment in the past 2 years (i.e. with use of disease modifying agents, corticosteroids or immunosuppressive drugs). Replacement therapy (eg., thyroxine, insulin, or physiologic corticosteroid replacement therapy for adrenal or pituitary insufficiency, etc.) is not considered a form of systemic treatment.
10. Has known history of, or any evidence of active, non-infectious pneumonitis.
11. Has an active infection requiring systemic therapy.
12. Has a history or current evidence of any condition, therapy, or laboratory abnormality that might confound the results of the trial, interfere with the subject's participation for the full duration of the trial, or is not in the best interest of the subject to participate, in the opinion of the treating investigator.
13. Has known psychiatric or substance abuse disorders that would interfere with cooperation with the requirements of the trial.

14. Is pregnant or breastfeeding, or expecting to conceive or father children within the projected duration of the trial, starting with the pre-screening or screening visit through 120 days after the last dose of trial treatment.
15. Has received prior therapy with an anti-PD-1, anti-PD-L1, or anti-PD-L2 agent.
16. Has a known history of Human Immunodeficiency Virus (HIV) (HIV 1/2 antibodies).
17. Hepatitis B virus positive subjects (defined as HBsAg positive and/or detectable HBV DNA).
 - Participants who are HBsAg positive are eligible if they have received HBV antiviral therapy for at least 4 weeks and have undetectable HBV viral load prior to enrollment.
 - Participants should remain on anti-viral therapy throughout study intervention and follow local guidelines for HBV anti-viral therapy post completion of study intervention.
18. Hepatitis C virus positive subjects (defined as anti-HCV Ab positive and detectable HCV RNA).
 - Participants with history of HCV infection are eligible if HCV viral load is undetectable at screening.
 - Participants must have completed curative anti-viral therapy at least 4 weeks prior to randomization.
19. Concurrent active Hepatitis B (defined as HBsAg positive and/or detectable HBV DNA) and active Hepatitis C virus (defined as anti-HCV Ab positive and detectable HCV RNA) infection.
20. Has received a live vaccine within 30 days of planned start of study therapy.

Note: Seasonal influenza vaccines for injection are generally inactivated flu vaccines and are allowed; however intranasal influenza vaccines (e.g., Flu-Mist®) are live attenuated vaccines, and are not allowed.

21. Has received organ transplantation.

5.2 Trial Treatments

The treatment to be used in this trial is outlined below in Table 2.

Table 2 Trial Treatment

Drug or radiotherapy	Dose/Potency	Dose Frequency	Route of Administration	Regimen/Treatment Period	Use
Cisplatin	30 mg/m ²	QW	IV infusion	Day 1 of each week for 2 weeks, starting within 8 weeks after esophagectomy.	Adjuvant CRT
Radiotherapy	180-200 cGy	QD (Monday to Friday)		Total 10-13 fractions	Adjuvant CRT
Pembrolizumab	200 mg	Q3W	IV infusion	Day 1 of each 3 week cycle for 18 cycles, starting within 4 weeks after completing adjuvant cisplatin-CRT	Experimental

5.2.1 Dose Selection/Modification

5.2.1.1 Dose Selection

The rationale for selection of doses to be used in this trial is provided in Section 4.0 – Background and Rationale.

Details on preparation and administration of pembrolizumab (MK-3475) are provided in the Pharmacy Manual.

5.2.1.2 Dose Modification (Escalation/Titration/Other)

Adverse events (both non-serious and serious) associated with pembrolizumab exposure may represent an immunologic etiology. These adverse events may occur shortly after the first dose or several months after the last dose of treatment. Pembrolizumab must be withheld for drug-related toxicities and severe or life-threatening AEs as per 3 below. See Section 5.6 for supportive care guidelines, including use of corticosteroids.

Table 3.1 Dose Modification Guidelines for Pembrolizumab-Related Adverse Events

Toxicity	Hold Treatment For Grade	Timing for Restarting Treatment	Treatment Discontinuation
Diarrhea/ Colitis	2-3	Toxicity resolves to Grade 0-1	Toxicity does not resolve within 12 weeks of last dose or inability to reduce corticosteroid to 10 mg or less of prednisone or equivalent per day within 12 weeks
	4	Permanently discontinue	Permanently discontinue

Toxicity	Hold Treatment For Grade	Timing for Restarting Treatment	Treatment Discontinuation
AST, ALT, or Increased Bilirubin	2 (AST/ALT : 3-5 x upper limit of normal [ULN]; bilirubin: 1.5-3 x ULN)	Toxicity resolves to Grade 0-1.	Toxicity does not resolve within 12 weeks of last dose or inability to reduce corticosteroid to 10 mg or less of prednisone or equivalent per day within 12 weeks
	3-4	Permanently discontinue	Permanently discontinue
Type 1 diabetes mellitus (if new onset) or Hyperglycemia	T1DM or 3-4	Hold pembrolizumab for new onset Type 1 diabetes mellitus or Grade 3-4 hyperglycemia associated with evidence of beta cell failure	Resume pembrolizumab when patients are clinically and metabolically stable
Hypophysitis	2-4	Toxicity resolves to Grade 0-1. Therapy with pembrolizumab can be continued while endocrine replacement therapy is instituted	Toxicity does not resolve within 12 weeks of last dose or inability to reduce corticosteroid to 10 mg or less of prednisone or equivalent per day within 12 weeks
Hyperthyroidism	3	Toxicity resolves to Grade 0-1	Toxicity does not resolve within 12 weeks of last dose or inability to reduce corticosteroid to 10 mg or less of prednisone or equivalent per day within 12 weeks
	4	Permanently discontinue	Permanently discontinue
Hypo-thyroidism		Therapy with pembrolizumab can be continued while thyroid replacement therapy is instituted	Therapy with pembrolizumab can be continued while thyroid replacement therapy is instituted
Infusion Reaction	2 ^a	Toxicity resolves to Grade 0-1	Permanently discontinue if toxicity develops despite adequate premedication
	3-4	Permanently discontinue	Permanently discontinue
Pneumonitis	2	Toxicity resolves to Grade 0-1	Toxicity does not resolve within 12 weeks of last dose or inability to reduce corticosteroid to 10 mg or less of prednisone or equivalent per day within 12 weeks
	3-4 or recurrent grade 2	Permanently discontinue	Permanently discontinue
Renal Failure or Nephritis	2	Toxicity resolves to Grade 0-1	Toxicity does not resolve within 12 weeks of last dose or inability to reduce corticosteroid to 10 mg or less of prednisone or equivalent per day within 12 weeks
	3-4	Permanently discontinue	Permanently discontinue
Myocarditis	3-4	Permanently discontinue	Permanently discontinue
Skin or suspicious Steven-Johnson syndrome (SJS) or toxic epidermal necrolysis (TEN)	3	Toxicity resolves to Grade 0-1	Toxicity does not resolve within 12 weeks of last dose or inability to reduce corticosteroid to 10 mg or less of prednisone or equivalent per day within 12 weeks

Toxicity	Hold Treatment For Grade	Timing for Restarting Treatment	Treatment Discontinuation
Skin	4	Permanently discontinue	Permanently discontinue
Confirmed SJS	3-4	Permanently discontinue	Permanently discontinue
Confirmed TEN	4	Permanently discontinue	Permanently discontinue
All Other Drug-Related Toxicity ^b	3 or Severe	Toxicity resolves to Grade 0-1	Toxicity does not resolve within 12 weeks of last dose or inability to reduce corticosteroid to 10 mg or less of prednisone or equivalent per day within 12 weeks
	Persistent 2 or 3 except endocrine dysfunction under endocrine supplement with good control; toxicity does not resolve within 12 weeks of last dose or inability to reduce corticosteroid to 10 mg or less of prednisone or equivalent per day within 12 weeks		Permanently discontinue
	Recurrent 3	Permanently discontinue	Permanently discontinue
	4	Permanently discontinue	Permanently discontinue

Note: Permanently discontinue for any severe or Grade 3 drug-related AE that recurs or any life-threatening event.

^a If symptoms resolve within one hour of stopping drug infusion, the infusion may be restarted at 50% of the original infusion rate (e.g., from 100 mL/hr to 50 mL/hr). Otherwise dosing will be held until symptoms resolve and the subject should be premedicated for the next scheduled dose; Refer to Table 4– Infusion Treatment Guidelines for further management details.

^b Patients with intolerable or persistent Grade 2 drug-related AE may hold study medication at physician discretion. Permanently discontinue study drug for persistent Grade 2 adverse reactions for which treatment with study drug has been held, that do not recover to Grade 0-1 within 12 weeks of the last dose.

Dosing interruptions are permitted in the case of medical / surgical events or logistical reasons not related to study therapy (e.g., elective surgery, unrelated medical events, patient vacation, and/or holidays). Subjects should be placed back on study therapy within 3 weeks of the scheduled interruption, unless otherwise discussed with the Sponsor. The reason for interruption should be documented in the patient's study record.

Table 3.2 Dose Modification Guidelines for Cisplatin-CRT-Related Adverse Events

Toxicities experienced at the day of starting a new cycle	Recommended Cisplatin-CRT Protocol Treatment	
	xRT	Cisplatin(30 mg/m ² /wk)
When ANC <2,000 – 1,500//µl, or Platelet <100K – 75K//µl	Continue	30 mg/m ² /wk
When ANC <1,500 – 1,000//µl, or Platelet <75K – 50K//µl	Continue	25 mg/m ² /wk

When ANC <1,000 – 500// μ l, or Platelet <50K – 25K// μ l	Continue	Hold
When ANC <500// μ l, or Platelet <25K// μ l, or febrile neutropenia, or active infection, or other life-threatening conditions	Hold	Hold
Serum creatinine >2 x ULN	Continue	Hold
Persistent \geq Gr. 3 toxicities, such as nausea or vomiting, despite of adequate supportive care	Continue	Hold

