- d. Pembrolizumab 200 mg will be administered as a 30 minute IV infusion every 3 weeks. Sites should make every effort to target infusion timing to be as close to 30 minutes as possible. However, given the variability of infusion pumps from site to site, a window of -5 minutes and +10 minutes is permitted (i.e., infusion time is 30 minutes: -5 min/+10 min).
- e. The Pharmacy Manual contains specific instructions for the preparation of the pembrolizumab infusion fluid and administration of infusion solution.

5.2.2.3 Visits during adjuvant therapy (also listed in 7.1.5.2):

- a. During the period of adjuvant cisplatin-CRT:
 - i. The patient will be seen on a weekly basis until 2 weeks after completing CRT.
 - ii. The patient will be evaluated for clinical symptoms and signs, hemogram, and biochemistry panel including bilirubin, AST, ALT, BUN, creatinine, Na, K, Ca, Mg, and other abnormalities found at screening check.
- b. During the period of adjuvant pembrolizumab therapy:
 - i. The patient will be seen on a 3-weekly basis for a total of 54 weeks.
 - ii. The patient will be evaluated for clinical symptoms and signs, hemogram, and biochemistry panels including bilirubin, AST, ALT, ALP, gamma-GT, LDH, albumin, BUN, creatinine, Na, Cl, K, Ca, Mg, glucose, and endocrine function (every 2 cycles) including TSH, T3, fT4, ACTH and cortisol.
 - iii. Pregnancy Test – Urine or Serum beta-HCG (for woman only), coagulation

test with PT/INR and aPTT, and urinalysis will be checked every 2 cycles.

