5.5 Concomitant Medications/Vaccinations (allowed & prohibited)

Medications or vaccinations specifically prohibited in the exclusion criteria are not allowed during the ongoing trial. If there is a clinical indication for one of these or other medications or vaccinations specifically prohibited during the trial, discontinuation from trial therapy or vaccination may be required. The investigator should discuss any questions regarding this with the Merck Clinical team. The final decision on any supportive therapy or vaccination rests with the investigator and/or the subject's primary physician.

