5.6 Rescue Medications & Supportive Care

5.6.1 Supportive Care Guidelines

Subjects should receive appropriate supportive care measures as deemed necessary by the treating investigator. Suggested supportive care measures for the management of adverse events with potential immunologic etiology are outlined below. Where appropriate, these guidelines include the use of oral or intravenous treatment with corticosteroids as well as additional anti-inflammatory agents if symptoms do not improve with administration of corticosteroids. Note that several courses of steroid tapering may be necessary as symptoms may worsen when the steroid dose is decreased. For each disorder, attempts should be made to rule out other causes such as metastatic disease or bacterial or viral infection, which might require additional supportive care. The treatment guidelines are intended to be applied when the investigator determines the events to be related to pembrolizumab.

Note: if after the evaluation the event is determined not to be related, the investigator does not need to follow the treatment guidance (as outlined below). Refer to Section 5.2.1 for dose modification.

It may be necessary to perform conditional procedures such as bronchoscopy, endoscopy, or skin photography as part of evaluation of the event.

- **Pneumonitis:**
 - For **Grade 2 events**, treat with systemic corticosteroids. When symptoms improve to Grade 1 or less, steroid taper should be started and continued over no less than 4 weeks.

- For **Grade 3-4 events**, immediately treat with intravenous steroids.
Administer additional anti-inflammatory measures, as needed.
- Add prophylactic antibiotics for opportunistic infections in the case of prolonged steroid administration.
- **Diarrhea/Colitis:**

Subjects should be carefully monitored for signs and symptoms of enterocolitis (such as diarrhea, abdominal pain, blood or mucus in stool, with or without fever) and of bowel perforation (such as peritoneal signs and ileus).

 - All subjects who experience diarrhea/colitis should be advised to drink liberal quantities of clear fluids. If sufficient oral fluid intake is not feasible, fluid and electrolytes should be substituted via IV infusion. For Grade 2 or higher diarrhea, consider GI consultation and endoscopy to confirm or rule out colitis.
 - For **Grade 2 diarrhea/colitis**, administer oral corticosteroids.

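### Table 3.1 allows pembrolizumab to restart at Grade 0-1 with no steroid condition, the point at which 5.6.1 only begins a taper; separately, 5.5.2 bars the anti-emetic steroid that 5.2.2.1 allows

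*Combined protocol and SAP*

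**What the plan says.** **Restart.** In Table 3.1 (5.2.1.2), eight rows give "Toxicity resolves to Grade 0-1" as the restart condition and carry a 10 mg/day steroid limit as a reason to stop. They are diarrhea/colitis; AST, ALT or bilirubin; hypophysitis; Grade 3 hyperthyroidism; Grade 2 pneumonitis; Grade 2 renal failure or nephritis; Grade 3 skin or suspected SJS/TEN; and Grade 3 or severe other toxicity. Hypophysitis adds that dosing can continue during endocrine replacement. No restart cell states a steroid dose. The stopping text reads "inability to reduce corticosteroid to 10 mg or less of prednisone or equivalent per day within 12 weeks". It stands in the discontinuation column and once more in a sub-row for other toxicity, where it also leads to permanent discontinuation.

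**Taper.** For pneumonitis, 5.6.1 says: "When symptoms improve to Grade 1 or less, steroid taper should be started and continued over no less than 4 weeks". It gives the same rule for colitis, hypophysitis, Grade 3-4 hyperthyroidism, hepatic events and renal events. Its introduction warns: "Note that several courses of steroid tapering may be necessary as symptoms may worsen when the steroid dose is decreased".

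**Dosing.** Under 5.2.2.2, "Pembrolizumab 200 mg will be administered as a 30 minute IV infusion every 3 weeks", with 3 days' tolerance either side of each Day 1.

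**Steroid prohibition.** 5.5.2 bars systemic glucocorticoids during the Screening and Treatment Phase. Its exceptions are immune-type events of clinical interest and, after consultation with the sponsor, physiologic doses. Subjects who need a barred treatment are to be removed. 5.2.2.1 lists steroid among the anti-emetics an investigator may give with cisplatin.

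**The concern.** A Grade 0-1 reading on treatment-dose steroid does not show that the event would stay there on less steroid, and 5.6.1 itself expects that it may not. If pembrolizumab is given during the taper and the event flares, nobody can say whether the steroid reduction or the new dose caused it. The answer matters to the patient, because the note to Table 3.1 says: "Permanently discontinue for any severe or Grade 3 drug-related AE that recurs or any life-threatening event". Recurrent Grade 2 pneumonitis also ends treatment. An early restart could therefore cost a patient the remaining cycles, and it would blur the toxicity data, which are a secondary objective.

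The anti-emetic conflict is simpler. Two sections give opposite instructions for the same drug in the same treatment period. Read literally, a patient given an allowed anti-emetic has taken a prohibited medication, and the stated consequence is removal.

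**Working it through.** The plan states no figure to reproduce, so the check sets the texts side by side and adds timing arithmetic.

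**Inputs.** Restart at Grade 0-1 (Table 3.1). Taper starts at Grade 1 or less and lasts at least 4 weeks = 28 days (5.6.1). Dosing interval 3 weeks = 21 days, tolerance +3 days (5.2.2.2). 26 patients (8.2.1), 2 cisplatin doses each (Table 2).

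**Step 1: rows affected.** Eight rows pair a Grade 0-1 restart with the 10 mg stopping text. Six of them have a taper in 5.6.1; skin and other toxicity do not. The Grade 2 infusion-reaction row also restarts at Grade 0-1 but carries no 10 mg text, so it is outside the point.

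**Step 2: taper left at the next scheduled dose.** Call the Grade 0-1 reading taper day 0. The next scheduled dose falls on day d, with d from 0 to 21.
- Days left = 28 − d: from 28 − 21 = 7 to 28 − 0 = 28.
- With the +3-day tolerance, d can reach 24, leaving 28 − 24 = 4.

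So a patient with one of these six toxicities who is managed under 5.6.1 and restarted at the next scheduled dose is still on steroid, even with the shortest taper.

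**Step 3: is the dose above 10 mg/day?** The documents give neither starting dose nor taper shape. As an assumption, take a linear taper to zero over 28 days from D mg/day: dose on day d = D × (28 − d)/28.
- Day 0: D = 40 gives 40 mg; D = 80 gives 80 mg.
- Day 21: 40 × 7/28 = 10 mg; 80 × 7/28 = 20 mg.

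Over this assumed range, the dose at restart runs from 10 to 80 mg/day. A lower starting dose could put it below 10.

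**Step 4: does the 12-week limit prevent this?** Scheduled dose days at weeks 3, 6 and 9 after the last dose precede week 12. That is at most three, since doses due while toxicity is unresolved are held. A limit that acts at week 12 cannot bar a restart before then.

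**Step 5: scheduled doses within a minimum taper (days 0 to 27).** If the first falls on days 0-6, the next (d + 21) is also inside, giving 2. If it falls on days 7-20, d + 21 is at least 28, giving 1. A patient already at or below 10 mg/day loses none. A restart limit of 10 mg/day would therefore delay 0 to 2 doses.

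**Step 6: anti-emetic steroid.** 7.1.5.2 lists cisplatin-CRT under the Treatment Period, and the Trial Summary (1.0) counts it as treatment, so 5.5.2 covers it. Neither exception in 5.5.2 fits an anti-emetic. Upper bound: 26 × 2 = 52 cisplatin doses. Steroid is one of four example anti-emetics given at discretion, so the range is 0 to 52.

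**The case against.** The strongest reply is that each row should be read whole. Pairing a Grade 0-1 restart with a need to reach 10 mg within 12 weeks implies that steroid is expected to come down during the hold. The table is headed as guidelines, and 5.6.1 calls its measures suggestions. All of that is fair as to intent. But 5.2.1.2 makes withholding mandatory according to this table, so it is the working hold-and-restart rule, and the restart cell lacks the condition.

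Several stronger readings are tempting, and the documents do not support them:
- *The protocol forces re-dosing on high-dose steroid.* It only permits a restart; nothing compels one.
- *The patient is re-dosed on an assessment that predates the taper.* 5.2.2.2 requires the Day 1 assessments before each dose, the flow chart schedules adverse event review at each pembrolizumab cycle, and 7.1.3 requires acceptable laboratory results. Only a same-day restart precedes all tapering.
- *Restart is laxer than entry.* Exclusion 5 covers a patient who "is receiving systemic steroid therapy or any other form of immunosuppressive therapy within 7 days prior to the first dose of trial treatment". That first dose is cisplatin-CRT, not pembrolizumab, so the comparison does not bear on a pembrolizumab restart.
- *5.5 forbids the steroid that 5.6.1 prescribes.* 5.5 opens with "Medications or vaccinations specifically prohibited in the exclusion criteria are not allowed during the ongoing trial", but its own subsection 5.5.2 states the exceptions. The reference there to events of clinical interest fits poorly with the two items in 7.2.3.2, but that list is introduced as non-exhaustive and 5.6.1 directs steroid use. The mismatch is clerical.

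On the anti-emetic, 5.2.2.1 is the more specific text, 5.5.1 allows treatment needed for a subject's welfare, and 5.5 leaves the final decision on supportive therapy to the investigator and/or primary physician. In practice the steroid would probably be given. The contradiction on the page remains.

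**Conclusion.** Both parts hold, at minor severity.

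Table 3.1 permits pembrolizumab to restart at the moment 5.6.1 begins a taper for six toxicities. At the next scheduled dose, 7 to 28 days of a minimum taper remain (at least 4 with the window). This assumes management under 5.6.1, a 28-day taper and restart at that visit. Re-dosing above 10 mg/day is possible, but whether it occurs depends on a starting dose the documents do not give. They give no immune-event rate either, so the number of patients affected is unknown.

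5.5.2 and 5.2.2.1 contradict each other on anti-emetic steroid, for 0 to 52 cisplatin doses.

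A reader might infer a threat to the primary result. There is none: neither part changes the 1-year RFS test, the sample size, the significance level or the power.

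**What to change.** 1. In the eight Table 3.1 restart cells identified above, keep the Grade 0-1 condition and add: *and corticosteroid dose no higher than 10 mg/day prednisone equivalent*. Keep the endocrine-replacement sentence for hypophysitis. The sub-row for persistent other toxicity has no restart to amend.
2. In 5.5.2, exempt anti-emetic steroid given with cisplatin under 5.2.2.1. The term for immune events could be tidied in the same edit.

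The cost is wording in eight cells and one exemption, with no change to sample size, visits or endpoints. The clinical price is a delay of 0 to 2 scheduled doses with a minimum taper, and more with a longer one. The 12-week stopping rule already exists. The steroid clause does not say when its 12 weeks begin; if they run from the last dose, an event at Grade 0-1 by week 12 − 4 = 8 leaves time for a full minimum taper.
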